Eligibility criteria will include 1) self-identify as Hispanic or Latino, 2) age 18 to 70 years, 3) receive primary care at one of the participating clinical sites, 4) at least one office visit within the previous 12 months to the primary care site, 5) diagnosis of T2D in the medical record, 6) T2D diagnosis for six months or longer, 7) most recent hemoglobin A1c \geq 8%, and 8) intention to continue to receive medical care at the recruitment clinic for the next six months. The value of 8% is higher than the goals established by the American Diabetes Association Guidelines (hemoglobin A1c<7%)⁹⁸, but lower than the definition of poorly controlled T2D established by the Center for Medicare & Medicaid Services Core Quality Measures Collaborative (hemoglobin A1c>9%)⁹⁹. It is common practice to increase an individual patient's goal hemoglobin A1c value in the context of clinical and social co-morbidities, but this goal value rarely exceeds 8%. Furthermore, the Minnesota Department of Health

has defined poorly controlled T2D as hemoglobin A1c \geq 8% for the purposes of mandatory reporting by clinical sites across the state¹⁰⁰. Therefore, we will use this value in keeping with common clinical practice to determine eligibility for the study.

The first step in screening for eligible participants is identification of Hispanic patients at both study sites with T2D. Per state-wide reporting mandates, each site maintains registries of their primary care patients with diabetes and the most recent hemoglobin A1c value for each patient. The second step in screening is to identify Hispanic adults within the subset of patients with the most recent hemoglobin A1c \geq 8% at both sites. Both sites have identified mechanisms for accurately identifying eligible patients (see letters of support). *In our pilot study, we identified 3,025 eligible patients across both sites.* Based on our pilot data, we expect to recruit approximately 50% women. Children were not included because of perceived community need that resulted in an intervention created for adults, and because of the relatively higher prevalence of T2D among adults.

Recruitment, Enrollment, Randomization, and Retention

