Once eligible patients are identified from institutional registries, the next office appointment for any diabetes-related indication (e.g., chronic disease management provider visit, diabetes educator visit, dietitian visit, diabetes group class, etc.) will be recorded for each patient. These patients will be contacted by telephone by a language-congruent study staff member to introduce them to the study and to assess preliminary interest in participation. Patients will be sequentially recruited at their next office visit until the target accrual is reached. Patients may also be recruited, consented and participate in study activities over the phone.

A language-congruent study staff member will confirm eligibility criteria with the patient and obtain written informed consent in an exam or private room before or immediately after their office appointment. Study staff will then obtain a baseline survey and biometric assessment (see measures) followed by randomization procedures (stratified by gender) and delivery of the digital storytelling intervention (for the intervention group). Each site has developed slightly different protocols for effective recruitment and intervention implementation based on lessons learned from the pilot study. Based on data from our pilot, we expect recruitment and enrollment to occur over a period of no more than 24 months across all sites with the following distribution:

- Hennepin Healthcare: N=240 participants enrolled.
 - Medicine Clinic
 - East Lake Clinic
 - Richfield Clinic
- Mountain Park Health Center: N=215 participants enrolled.

Participant retention will be facilitated in five ways. First, potential participants will confirm the eligibility criteria stating that they expect to receive medical care at the recruitment clinic for at least the next six months (above). Second, appointment cards for both subsequent study visits will be provided to participants after they have completed enrollment. Third, language-congruent study staff will contact patients by phone to remind them about upcoming study visits. Fourth, participants who do not return phone calls from study staff will be sent a letter asking them to call the study coordination to reschedule the appointment. Fifth, participants will receive remuneration at enrollment and at the of the 3 month visit.

Interventions

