Secondary outcome measures. Diabetes self-management behaviors will be assessed with the Summary of Diabetes Self-Care Activities Measure (SDSCA)¹¹². This is a brief survey instrument to assess the following domains: general diet, specific (diabetes) diet, physical activity, diabetes medication use, and blood glucose monitoring. In a 2009 review of psychometric tools to assess diabetes self-management behaviors, the SDSCA was one of only three instruments to meet all appraisal criteria¹¹³. The SDSCA is also the most commonly used instrument for these domains worldwide, with good validity evidence in several languages, including Spanish^{114,115}. Furthermore, we used this instrument with Hispanic/Latino patients during the early phase (Step 1) for this project²². The SDSCA will be administered by the same language-congruent study staff at each measure.

Seated blood pressure measurements (systolic and diastolic) will be made on the right arm using an automated BP Tru BPM-200 device after sitting quietly for five minutes¹¹⁶. Blood pressure will be measured three times; the average of the second and third readings will be used in statistical analyses. Most recent values may also be abstracted from the electronic medical records.

Weight will be measured to the nearest 0.1 kg using a single portable scale (Seca 880 Digital Floor Scale). Height will be measured to the nearest 0.1 cm at baseline only using a stadiometer. Participants will be asked to remove shoes prior to both measurements. Body mass index (BMI) is calculated as weight (kg)/height squared (m²). Most recent values may also be abstracted from the electronic medical records.

Total cholesterol, HDL cholesterol, and triglycerides will be measured from the same blood sample used to derive the outcome measure. LDL-cholesterol will be calculated for each participant based on these values: LDL-cholesterol=total cholesterol – HDL cholesterol – (triglycerides/5).

- Baseline LDL-cholesterol values will be drawn at the baseline study visit. LDL-cholesterol values drawn up to two weeks prior to the baseline visit date as part of usual clinical care may be used as the baseline LDL-cholesterol value. Recent values recorded as part of usual clinical care within a week prior to the study visit may be abstracted from the electronic medical records.

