- Cholesterol values at 3 months will be drawn at the 3 month study visit. Recent values recorded as part of usual clinical care within two weeks prior to the visit may be abstracted from the electronic medical records.
- Subsequent cholesterol levels will not be drawn or abstracted.

The total volume of whole blood drawn from each participant will be approximately 8 mL (3 mL for hemoglobin A1C testing and 5 mL for cholesterol testing) when visiting the lab. Over-the-counter A1c Test kits will be mailed to patients unable to visit the lab. Study staff will call patients to confirm reception of kit and go through the instructions.

All study tasks can be completed in-person in the clinical setting, virtually, or a combination of both, to accommodate the growing interest of patients to perform tasks virtually, when possible. This flexibility is noted in the Study Tasks Table below.

The number of diabetes-related office visits will be abstracted from the electronic medical records and categorized as a visit with a primary care provider, endocrinologist, pharmacist, care manager, diabetes educator, dietician, community health worker or promotora. These visits will be recorded for the six-month interval before and after intervention (or control) delivery.

Theory-based measures. We will measure diabetes-related self-efficacy with the Diabetes Self-Efficacy Scale ($\alpha=0.85$)¹¹⁷, used in other studies with Spanish-speaking patients¹¹⁸, including one from our study team that we used to generate preliminary data for this proposal²². We will measure diabetes-related outcome expectations with the Outcome Expectancies Questionnaire¹¹⁹, and social support for diabetes with items from the Diabetes Care Profile¹²⁰, which we also used in our pilot study.

Story identification and transportation will be assessed through a 14-item scale developed by Larkey and colleagues that demonstrated very good construct validity among Hispanic, Spanish-speaking populations^{121,122}, with initial predictive validity on the transportation (emotional engagement) scale⁸⁴.

Intervention follow-up exposure. During follow-up measures, we will assess the number of times each participant viewed the digital storytelling videos and whether they viewed it with friends or family. This will provide an assessment of intervention dose for the intervention group following the supervised viewing at enrollment.

Table 2. Measures

Data Collected	Baseline	6 weeks	3 months	6 months

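### LDL-cholesterol is calculated as TC − HDL − TG/5 at every triglyceride level, with no limit, fasting condition or fallback (minor; one secondary outcome)

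*Combined protocol and SAP*

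**What the plan says.** Under Measures, Secondary outcome measures, the protocol states: "Total cholesterol, HDL cholesterol, and triglycerides will be measured from the same blood sample used to derive the outcome measure". It continues: "LDL-cholesterol will be calculated for each participant based on these values", and gives the formula TC − HDL − TG/5. No units are stated; the divisor 5 implies mg/dL.

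Routine results can replace study samples. At baseline, "LDL-cholesterol values drawn up to two weeks prior to the baseline visit date as part of usual clinical care may be used". At 3 months, "Recent values recorded as part of usual clinical care within two weeks prior to the visit may be abstracted from the electronic medical records". How the clinic obtained those values is not specified.

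LDL is a named secondary outcome, measured at baseline and 3 months (Table 2). Under Data analysis plan, Secondary analyses, it is compared between arms by t-test and by repeated measures models. Eligibility (Study Participants) rests on a type 2 diabetes diagnosis and a "most recent hemoglobin A1c" of at least 8%, with no triglyceride criterion. The section on training and quality assurance has the statistician look each month for missing and outlying data, but sets no action for an implausible LDL.

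**The concern.** The formula estimates the cholesterol carried in VLDL as a fixed fifth of triglycerides. That approximation fails at high triglycerides, and the formula shows this itself: if TG is large enough the result is negative, which no concentration can be. Laboratories conventionally stop using it at about 400 mg/dL. That figure is not in the documents, but the need for some limit does not depend on it.

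Followed as written, the plan puts such results into the LDL t-test. The outlier check would probably catch a negative value, but not one that is too low yet still plausible. Raised triglycerides are plausible in poorly controlled type 2 diabetes. The video promotes diet, activity and medication adherence, which could change triglycerides, so the error need not stay equal between arms.

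**Working it through.** **Inputs from the documents.** The formula and its application to each participant (Secondary outcome measures); 200 analysed per group and an effect of 0.28 SD (Sample size considerations, stated for A1c). The documents give no triglyceride distribution, LDL standard deviation or target LDL difference; pilot Table 1 has only age, sex and A1c. All lipid values below are assumptions, in mg/dL.

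**1. Where the formula gives impossible values.** TC − HDL − TG/5 < 0 exactly when TG > 5 × (TC − HDL).

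| Assumed TC / HDL | TG 150 | TG 400 | TG 600 | TG 800 | TG 1,000 | Negative above TG |
|---|---|---|---|---|---|---|
| 180 / 40 | 110 | 60 | 20 | −20 | −60 | 5 × 140 = 700 |
| 200 / 40 | 130 | 80 | 40 | 0 | −40 | 5 × 160 = 800 |
| 240 / 40 | 170 | 120 | 80 | 40 | 0 | 5 × 200 = 1,000 |

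These are outputs of the formula, not errors against true LDL. Only the negative entries are wrong on their face.

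**2. Noise, if the error is equal in both arms.** Suppose a share q of each arm has LDL too low by b, unrelated to true LDL. Each arm's mean shifts by −q × b and the expected difference is unchanged. The variance becomes SD² + q(1 − q)b².

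The plan gives no LDL power to reproduce, so its A1c setting serves as the starting point: 0.28/√(2/200) = 2.80; 2.80 − 1.96 = 0.84; power 80.0%, as stated for A1c.

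With assumed q of 2–15%, b of 20–60, LDL SD of 35–40 and 200 lipid panels per arm:

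- Mildest case (q = 2%, b = 20, SD 40): mean shift −0.4; SD = √(1,600 + 0.0196 × 400) = 40.1; power 79.8%.
- Most severe case (q = 15%, b = 60, SD 35): mean shift −9.0; SD = √(1,225 + 0.1275 × 3,600) = 41.0; power 66.6%.

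**3. Bias, if triglycerides diverge.** Suppose the intervention shrinks the average error q × b by a fraction s in its own arm only. The bias in the LDL difference is q × b × s. With assumed q of 5–10%, b of 20–60 and s of 10–25%, it runs from 0.05 × 20 × 0.10 = 0.1 to 0.10 × 60 × 0.25 = 1.5 mg/dL. The standard error of the difference is SD × √(2/200), or 3.5 to 4.0 mg/dL for SD 35–40.

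**The case against.** The best defence is that this is one secondary outcome on which the trial is not powered, and that the harm cannot be shown from the documents. Much of that stands. Several stronger readings are tempting, and the documents do not support them:

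- **That the trial selects for high triglycerides.** It selects on A1c.
- **That a count of bad values can be given.** Taking 5–10% of about 400 analysed participants would give 20 to 40, but the share is a guess. Participants who cannot visit the laboratory are mailed A1c kits, with no remote lipid test described, and other values may come from the record. How many LDL values rest on this formula is unknown.
- **That the falling figures in the table measure the error.** At fixed TC and HDL, true LDL also falls as more cholesterol is carried in VLDL.
- **That the LDL comparison is biased against the intervention.** That needs triglycerides to fall more in that arm, for which there are no data. Under the assumptions above the bias is below half a standard error.
- **That samples are non-fasting because patients are seen around clinic visits.** The sentence "obtain written informed consent in an exam or private room before or immediately after their office appointment" concerns consent. Silence on fasting shows only that fasting status is not controlled.

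The monthly outlier check is a partial safeguard at the extreme. What the defence does not answer is that the protocol states a rule for everyone, that the rule must fail above some triglyceride level, and that nothing says what happens then.

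**Conclusion.** The point holds as a minor one. The stated rule has no triglyceride limit, fasting condition or fallback, and can put unreliable values, in extreme cases impossible ones, into the LDL analysis. Negative results need triglycerides above about 700 to 1,000 mg/dL for the assumed lipid values; LDL that is too low but believable is the likelier problem.

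The size cannot be fixed from the documents. Under the assumptions shown, equal errors cost between almost nothing and about 13 percentage points of power (80.0% to 66.6%) for an LDL difference of 0.28 SD. Bias arises only if triglycerides diverge between arms. That high-triglyceride values are falsely low rests on general knowledge of the TG/5 term. The A1c analysis and sample size are unaffected.

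**What to change.** In Secondary outcome measures, state that the TG/5 formula is not used at or above a prespecified triglyceride limit (for example 400 mg/dL). Above it, use a laboratory direct LDL where one is already reported; otherwise treat calculated LDL as unavailable. Apply the rule blind to arm and report the number affected by arm. Record fasting status where known, and the method behind abstracted LDL values.

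Analyse non-HDL cholesterol (TC − HDL) for all participants with a lipid panel as the accompanying lipid measure. It uses values already collected and has no triglyceride term.

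The cost is a few sentences, one derived variable and no new blood. There are two downsides. Some LDL values become missing, and at 3 months that missingness depends on a triglyceride value measured after randomisation, so it can be informative if the intervention changes triglycerides. LDL should therefore be shown with and without the exclusion and read beside non-HDL. Non-HDL also adds a comparison to secondary analyses that carry no multiplicity adjustment, and it does not recover LDL itself, so it should be labelled as supporting.

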Implementation adaptation. There is increasing recognition of the need for transparent reporting on adaptations of intervention implementation to fit local contexts^{124,126}. The “core” component of the intervention for this study, i.e., viewing the video, will be standard across both sites. However, during the pilot study, we learned that the timing of intervention delivery (e.g., before or after office visit), associated visit type (e.g., during diabetes classes versus during provider visits), and recruitment procedures will vary slightly between sites. We will conduct semi-structured interviews with study staff and clinical staff at both sites to assess rationale for site-specific adaptations across each of these domains, and to further elucidate generalizable best practices for implementation of this intervention. These various conditions (timing, visit type) as well as study site will be tracked and assessed for any moderating effects.

Intervention reach and adoption. Intervention reach will be reported as the percentage of invited patients who choose to participate. The differential demographic and disease-specific characteristics of these two groups will be reported and compared. Intervention adoption will be reported as the percentage of eligible patients invited to participate at each site. These groups will likewise be compared. Site-specific differences in reach and adoption will be explored through interviews with staff at each site as described above.

Sample size considerations

Our preliminary data suggest that we may expect a moderate effect size for the intervention (25%-50% times the standard deviation). This is similar to two recent meta-analyses^{127,128} of related work that informs the effect size we can expect to observe in the proposed study. The first meta-analysis of 11 randomized trials examined the efficacy of diabetes self-management education added to usual care among Hispanic patients in primary care settings, which produced an average hemoglobin A1c reduction of 0.25 standard deviations¹²⁷. The second meta-analysis of 20 randomized trials evaluated the efficacy of diabetes self-management education among

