racial/ethnic minority populations, which showed a similar hemoglobin A1c reduction of 0.31 standard deviations¹²⁸. While these effects sizes are smaller than that of our pilot study, we have picked the more conservative (lower) estimate of effect size to ensure ample sample size. Hence, we can expect an effect likely to be between 0.25 and 0.31 standard deviation for the type of intervention proposed. Required sample sizes for an independent samples t-test to detect these two effect sizes, assuming 80% power, a two-tailed alternative and a 5% Type I error rate, are 252 and 145 patients per group, respectively. With 200 patients per group, we will have 80% power to detect an effect size of 0.28 standard deviations via the independent samples t-test. Accounting for approximately 12% loss to follow-up, we intend to recruit 225 patients in each group, for a total sample size of 450 participants.

Data analysis plan

Aim #1: Evaluate the efficacy of a community-derived digital storytelling intervention among Hispanic adults with poorly controlled T2D.

The primary analysis will be an independent samples t-test between the group average hemoglobin A1c values at 3 months. A two-sided alternative with a 5% type I error rate will be employed.

Supplementary analysis for the primary endpoint. Repeated measures modeling of the individual time point A1c values (including chart abstracted values at approximately 6 months) will allow for a more detailed investigation to the timing of the impact of the intervention by including all time points (including baseline). Profile analysis (Srivastava) will further assess for difference in overall means, time point, and treatment by time interactions. Covariates indicated above including demographics and clinical covariates will be included in the repeated measures and profile analysis models to assess the sensitivity of the primary analysis conditional on these potential concomitant (mediating) influences.

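### The sample size is described as ample and based on the lower effect estimate, but 200 evaluable patients per group is sized for 0.28 SD and has about 70% power at 0.25 SD

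*Combined protocol and SAP*

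**What the plan says.** All of this is in the combined protocol and SAP, under Sample size considerations, unless another section is named.

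- Two meta-analyses inform the effect size. The first covers self-management education added to usual care for Hispanic patients in primary care, "which produced an average hemoglobin A1c reduction of 0.25 standard deviations". The second covers racial and ethnic minority populations, "which showed a similar hemoglobin A1c reduction of 0.31 standard deviations".
- After noting that both are smaller than the pilot effect (0.37 SD, under Preliminary data), the plan says "we have picked the more conservative (lower) estimate of effect size to ensure ample sample size".
- It concludes that "we can expect an effect likely to be between 0.25 and 0.31 standard deviation for the type of intervention proposed".
- It gives 252 per group for 0.25 SD and 145 per group for 0.31 SD, "assuming 80% power, a two-tailed alternative and a 5% Type I error rate".
- It then adopts a different number: "With 200 patients per group, we will have 80% power to detect an effect size of 0.28 standard deviations". Allowing for about 12% loss, it recruits 225 per group.
- The Data analysis plan matches on the test: "The primary analysis will be an independent samples t-test between the group average hemoglobin A1c values at 3 months". On the error rate it says "A two-sided alternative with a 5% type I error rate will be employed".

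Power at 0.25 SD with the adopted 200 per group is not stated.

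**The concern.** The paragraph gives a reason for the sample size and then a sample size that does not follow from it. A reader who takes the rationale at face value will believe the bottom of the expected range is covered at the 80% target. It is not: the adopted number is the one for 0.28 SD.

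This matters because 0.25 SD is no remote pessimistic value. The plan calls it likely, and it comes from the meta-analysis closer to this trial's population and setting. If the true effect is 0.25 SD, the primary test misses it about 3 times in 10, against the 2 in 10 that an 80% target implies. A reader who believes the trial was conservatively sized could give a non-significant result more weight against such an effect than the design supports.

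**Working it through.** **Inputs.** Two-sided alpha 0.05, target power 80%, independent-samples t-test, equal groups and effects in SD units (Sample size considerations; test and error rate confirmed in the Data analysis plan). Evaluable n is 200 per group. Expected effects are 0.25 to 0.31 SD, with midpoint (0.25 + 0.31)/2 = 0.28.

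**Step 1. Reproduce the plan's figures.** By the normal approximation, n per group = 2(1.960 + 0.842)²/d² = 15.70/d².

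| Effect (SD) | Plan, n per group | Normal approximation | Noncentral t |
|---|---|---|---|
| 0.25 | 252 | 251.2, so 252 | 252.1 |
| 0.28 | 200 | 200.2, so 201 | 201.2 |
| 0.31 | 145 | 163.3, so 164 | 164.3, so 165 |

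The figures for 0.25 and 0.28 SD reproduce. The effect detectable with 80% power at 200 per group is 2.802 × √(2/200) = 0.280 SD (0.281 by noncentral t). The 145 does not reproduce: it is the number for about 0.33 SD, and at 0.31 SD it gives about 75% power. The adopted 200 does not depend on it.

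**Step 2. Power at the adopted sample size.** Power ≈ Φ(d√(n/2) − 1.960). With n = 200, √(n/2) = 10.

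- 0.25 SD: Φ(2.50 − 1.96) = Φ(0.54) = 70.5% (noncentral t 70.3%)
- 0.28 SD: Φ(2.80 − 1.96) = Φ(0.84) = 80.0% (79.8%)
- 0.31 SD: Φ(3.10 − 1.96) = Φ(1.14) = 87.3% (87.1%)

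The shortfall against the plan's own requirement for 0.25 SD is 252 − 200 = 52 per group. The chance of missing a true 0.25 SD effect is 100 − 70.3 = 29.7%.

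**Step 3. Do other readings of the sample size change this?** Noncentral-t power at 0.25 SD:

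- 225 per group less 12%: 225 × 0.88 = 198, power 69.9%.
- The total of 455 given under Design Overview: 455/2 × 0.88 = 200.2 per group, power 70.4%.
- 225 per group with no loss at all: power 75.4%.

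None reaches 80%.

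**Step 4. What a non-significant result would say about 0.25 SD.** At 200 per group the standard error is √(2/200) = 0.10 SD and the 95% confidence half-width is about 0.197 SD. Estimates below 0.25 − 0.197 = 0.053 SD exclude 0.25 SD at that level. Estimates between about 0.053 and 0.197 SD are non-significant yet compatible with it.

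**The case against.** The strongest reply concerns the word lower. The sentence opens by comparing the meta-analyses with the pilot, and the next sentence concludes with a range, not with 0.25 SD. On that reading the authors preferred the smaller meta-analytic evidence to the pilot's 0.37 SD, and 0.28 SD is consistent with that. This stands as a fair reading. A reader might infer that the plan commits itself to 0.25 SD and then contradicts itself outright; the wording does not settle that. The claim of an ample sample remains, and it fails below 0.28 SD on either reading.

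Second, the plan is open about the facts. The 252 and the 0.28 SD basis appear within a few lines of the rationale. This also stands. A reader might infer a concealed or miscalculated power for the adopted design, but the documents do not support that: the stated 80% at 0.28 SD is right.

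Third, powering at the middle of an expected range is a legitimate choice, and nothing in the documents sets a futility rule or says how a null result will be read. That is accepted. The concern about over-reading is a risk to guard against, not something the plan proposes.

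Fourth, adjusting for baseline A1c could recover power. For assumed baseline to 3-month correlations of 0.3 to 0.6, power at 0.25 SD would be about 75% to 88%. The documents give no correlation, though, and the primary test is unadjusted; repeated-measures models are only supplementary.

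**Conclusion.** The point holds as a mismatch between a stated rationale and the adopted design. The trial is sized for 0.28 SD. At 0.25 SD, the bottom of the range the plan calls likely, power is about 70% against an 80% target, and the evaluable sample is 52 per group below the plan's own requirement. The result rests on the plan's stated test, alpha and effect range, and on 200 evaluable per group; replacing 200 with 198 changes power by less than half a percentage point.

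Two stronger conclusions are tempting and not supported. One is that the trial is invalid or must enrol more patients: 80% power at 0.28 SD is a defensible target if it is described as such. The other is that a non-significant result could never rule out 0.25 SD: an estimate below about 0.05 SD would exclude it at the 95% level.

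The point deserves correction because it concerns the sizing of the primary endpoint, but it does not undermine the trial.

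**What to change.** Under Sample size considerations, replace the sentence containing the rationale with:

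> The meta-analytic estimates (0.25 and 0.31 SD) are smaller than the pilot effect and were used in preference to it. The trial is sized for 0.28 SD, the middle of that range. With 200 evaluable per group, power is about 70% at 0.25 SD, 80% at 0.28 SD and 87% at 0.31 SD; a non-significant result does not by itself rule out an effect of 0.25 SD, and the confidence interval should be used to judge this.

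This keeps the useful comparison with the pilot. In the same edit, correct the 145 per group for 0.31 SD to about 165, so that it does not stand beside a power figure it contradicts.

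The cost is one reworded paragraph and a less favourable stated property. Sample size, primary test and conduct are unchanged.
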